The Effectiveness of Peer-to-Peer Community Support to Promote Aging in Place

Principal Investigator: [name]

Protocol Version Date: 10/30/2017

Coordinating Center: University of Wisconsin

Co-Investigators

[name]-University of Wisconsin
[name]- Alliance for Children and Families
[name]- Alpert Jewish Family and Children's Service
[name]- Community Place
[name]- Jewish Family Service of Los Angeles

Study Coordinator: [name]

Funding Sponsor: Patient Centered Outcomes Research Network (PCORI)

Statistical Considerations

In this section, we outline in detail the strengths of our proposed sampling and analysis plan and how it is designed to address and minimize the potential limitations of our study design. Specifically, we elaborate on how we plan to make our samples in the peer-support and standard community services group comparable, despite the fact we cannot randomize all participants; how we will control for differences across sites in our analyses; and how we will deal with missing data (including loss to follow-up).

Analysis Plan The mixed experimental and quasi-experimental, matched group comparison design allows us to conduct three different analyses to accomplish both Aims 1 and 2: (1) comparing the effectiveness of peer support to standard community services at 6 months combining data from all three sites; (2) analyzing the data from AJFCS and the combined data from the other two sites to assess the internal consistency of the effectiveness across the randomized and non-randomized designs but also to assess whether the effect size is different between the two components of the study design; (3) analyzing data from AJFCS to test whether peer-support is more effective when provided for 12 months compared to 6 months. For the third analysis using AJFCS data only, we will compare 12 vs. 6 month "dose"-levels of the peer-to-peer support intervention changes in the rates of health care utilization and nursing home placement and self-rated health, wellness, depression, and anxiety of between baseline and 12 months in group randomized to get peer support relative to changes in these same measures between 6 and 12 months in the group randomized to standard community services; as reminder this group received standard services for 6 months and then transitioned into receiving peer-support between 6 and 12 months (see Figure 3).

The primary analyses for comparative effectiveness will be based on two-sample independent tests such as t-test, Wilcoxon rank sum test, Fisher's exact test or chi-square test of the outcome measures. The choice of analytic method will depend on whether the outcome measures are continuous or categorical. These tests will be performed at a two-tailed significance level of 0.05 without adjustment for multiplicity. Health care utilization and nursing home placement rates and self-rated health, wellness, depression, and anxiety between the two groups will be compared using a two-sample test again at a two-tailed significance level 0.05.

Subsequent to the primary analyses, regression analyses will be performed for the same outcome measures adjusting for stratification factors and other potential confounders that might influence the outcomes, including an indicator for site. Linear or generalized linear models such as logistic and Poisson regression models will be used depending on the outcome measures. As the intermediary measures of health and overall wellness such as self-rated health, depression, and anxiety in Aim 2 may serve as important mediators of the effect of the peer-to-peer support intervention on the primary outcomes measures in Aim 1, we will use exploratory mixed-effects regression techniques and structural equation models to test and quantify whether and to what extent the effect of the intervention is mediated by intermediary measures of health and overall wellness. We expect missing data due to random drop-out of participants before month 12 and to a lesser extent loss due to death of participants before month 12. Missing data will be handled as per the recent National Research Council report on the topic.⁷⁷ Death before month 12 will be considered a competing event, and will be handled using the appropriate method.⁷⁸

Given the diverse nature of our sample, we plan to carry out the statistical analyses for Aims 1 and 2 for a limited number of subgroups. We will conduct subgroup analyses based on race/ethnicity (African American, Hispanic and non-Hispanic White), gender (male vs. female), age group (< 70, 70-80 and ≥ 80 years), and language (English- vs. Spanish-speaking) and by the three sites. These subgroup analyses will be conducted to evaluate the internal consistency of intervention effect, and subgroup by intervention interaction tests will be used to assess the internal consistency.

Randomization and matching In order to reduce potential bias further, participants from the AJFCS of Palm Beach will be allocated either to peer-to-peer support (Intervention) or standard community support (Control) in a 1:1 ratio using permuted block randomization, stratified by age, gender and race/ethnicity. Barring randomization in JFS of LA and Community Place of Greater Rochester, older adults already participating in peer-to-peer support and those on the waiting list will be matched on age, gender and race/ethnicity to mitigate potential differences between the two groups. In order to avoid reporting/ascertainment bias, calls will be made to all participating older adults and support staff at 3 and 9 months as outlined in Figure 4 above.

Sample Size Justification Given the total sample size of 720 at-risk older adults, the study has 0.80/0.85/0.90 power to detect the effect size of 0.209/0.223/0.242 for the primary outcome measure of the annualized rate of hospitalization, ED use and institutionalization at a two-tailed significance level 0.05. The effect size here is defined as the difference in the mean annualized rate of hospitalization, ED use and institutionalization between the two groups divided by the standard deviation of the annualized rate assumed to be common in the two groups. Due to random drop-out or loss to competing event of death, the study will have less power to detect the stated effect sizes or will have the stated power for larger effect sizes.

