Enrolling people in the study is a three step process. Step 1, is technically a pre-screen, we only want to upload people into DatStat who we think are eligible. If for whatever reason we find out that they are not eligible then we don't want them in the database. You can email [name] and she will delete their entry from DatStat. It is also a good idea for all RAs to keep a list of participants that have been deleted to ensure that you don't accidentally contact them again. Step 2 is the formal screening. If during the formal screening it turns out that they are not eligible then DatStat marks them as ineligible, and they will be removed from your workflow. They do not need to be formally exited from the study. Step 3 is when they sign the consent form during the baseline survey. Once they sign the consent form then, they are officially enrolled in the study. Moving forward, if for whatever reason the person withdraws consent, dies or meets a main study outcome that would be when you officially exit them from the study using the exit survey. The rule of thumb is we only exit people from the study who are officially enrolled, and people are only officially enrolled once they sign the consent form.

Updating or changing participant information once enrolled in study

When updating or changing participant information in Discovery, you can update participant information however you like, including assigning someone to the most accurate study group, prior to the participant signing the consent form. Once a participant signs a consent form, at that time we will consider all the information entered in Discovery to be updated and accurate. At this point some very critical variables such as study arm, race, age, gender, site, language, DOB, can never be changed, even if they are wrong. If at any time after the participant signs a

consent, you realize there is an error in one of these data categories you cannot change the information in Discovery but rather you need you to record that information in a participant log (a word document that you will keep on your computer) and you need to alert [name] of the change. Every few months [name] will ask for a copy of these participant logs. The participant log should include the Participant ID number, the person who made the change in the DatStat system, the original incorrect value and the new corrected value.

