Why is the participant leaving the study? (DATSTAT_EXITREASON)

Completed

Deceased

Censored (moved to a higher level of care- i.e. independent care to assisted living)

Unable to Continue (you should mark this answer if the person is too sick to continue)

Unable to Locate

Unwilling to Continue
Withdrawn by study staff
Unknown

What day did this person exit the study? (DATSTAT_EXITDATE)

What other information should we know about why this person left the study?
(DATSTAT_EXITCOMMENT)

Missing Data Points for a Participant

If study staff are not able to contact a participant within the appropriate window of data collection they have not exited the study but this is considered missing data. We will continue trying to contact the participant at every data collection point unless they contact us directly and ask to withdraw from the study. If research staff “miss” a data collection point, they should still try to collect the data but will have to follow the following protocol to ensure data is collected accurately:

Our DatStat workflow set up in your configuration is such that the time point gets updated when EITHER of the following occurs: 1) the survey for that timepoint gets submitted, OR 2) the time point goes out of window. For this participant, the 3 month call went out of window, and thus the timepoint got updated to 6 months.

In order to enter data for the 3 month survey at this point, the following must occur:

1. The participant must be edited and their time point set back to “3 months”
2. The current open survey (study task = “3 month survey”) must be closed by clicking Edit Survey next to the task in the Study Task grid, and changing the status to Final Incomplete
3. A new 3 month survey study task must be added. To do this, while in the study Task grid go to the Take Action menu and select Add Survey. Select the survey called “3 month Survey (Ad hoc)”. Schedule the survey, and select the Survey Pending status code, and click save. You may now use this task to enter your 3 month data. DO NOT do this until you’ve done steps 1 and 2.

Any time you make a change like this you need to mark down in your study log that you are making this change and mark down in your survey that this was collected out of window and the reason why. You also need to alert [name] that this change is made and she will record it in the data log,

Reentry into the study after exited**

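### If AJFCS was randomized as the SAP says, the 12- versus 6-month analysis of self-rated scores sets a 12-month change against a 6-month change and counts the unsupported change in months 0-6 as dose effect

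*SAP*

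**What the plan says.** The SAP (Statistical Considerations, Analysis Plan) lists as its third analysis "analyzing data from AJFCS to test whether peer-support is more effective when provided for 12 months compared to 6 months". The outcomes are "changes in the rates of health care utilization and nursing home placement and self-rated health, wellness, depression, and anxiety". For the immediate-support arm the change runs "between baseline and 12 months in group randomized to get peer support". It is assessed "relative to changes in these same measures between 6 and 12 months in the group randomized to standard community services". The SAP adds that "this group received standard services for 6 months and then transitioned into receiving peer-support between 6 and 12 months".

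The tests are two-sample tests at two-sided 0.05, followed by regressions that adjust for stratification factors, confounders and site. Under Randomization and matching, the SAP says AJFCS participants are randomized 1:1.

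The protocol describes AJFCS differently. Its AJFCS recruitment section and its Matching section have people already in the peer program matched with controls recruited from the community. They mention neither random allocation to support nor a start of support at month 6.

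On incomplete follow-up, the SAP says: "We expect missing data due to random drop-out of participants before month 12 and to a lesser extent loss due to death of participants". The protocol also ends follow-up for other reasons. Enrollment in Study says "if for whatever reason the person withdraws consent, dies or meets a main study outcome that would be when you officially exit them", and the exit reasons under Exiting the Study include "Censored (moved to a higher level of care- i.e. independent care to assisted living".

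**The concern.** A comparison of changes between randomized arms isolates the treatment only if both arms are measured from the same starting point over the same time. Here the immediate arm's change includes months 0-6 and the delayed arm's does not. Whatever happens to participants' scores in those six months regardless of support (decline, recovery, regression to the mean) enters one side only. Randomization makes the arms alike at baseline but does not protect a contrast built on different windows.

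This is the only planned test of whether longer support is more effective. For self-rated scores, drift alone could produce a dose difference where there is none, or hide a real one. For utilization and placement the problem is different: the SAP does not define what a change in a rate means over these windows. The follow-up periods differ there too, but the documents do not allow the size or direction of any bias to be worked out.

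**Working it through.** **The plan's own figure.** The only sample-size statement in the SAP is 720 participants, with power 0.80/0.85/0.90 for effect sizes 0.209/0.223/0.242 on the primary rate outcome. With 360 per arm and a two-sided 5% test, the normal approximation gives power 0.801/0.849/0.901, so it reproduces. No figure is given for analysis (3).

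**Expected value of the planned contrast (self-rated scores).** Let s1 and s2 be the mean change without support in months 0-6 and 6-12, and e12 and e6 the effects at month 12 of 12 and 6 months of support.

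- Immediate arm, months 0-12: e12 + s1 + s2
- Delayed arm, months 6-12: e6 + s2
- Difference: (e12 - e6) + s1

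If both arms are measured from baseline, both carry s1 + s2 and the difference is e12 - e6.

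**Does anything planned remove s1?** The named covariates do not, because s1 is present in one arm's window and absent from the other's, so it cannot be separated from arm. The mixed-effects models in the SAP are exploratory and meant for mediation. Dividing each change by its window length would also rescale the support effects.

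**Direction.** With higher scores better, decline without support works against the longer duration and improvement works in its favour.

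**Size.** The documents give no drift, no SD of change and no visit correlation, so these are assumed. From the documents: 150 per arm (protocol, AJFCS recruitment goal) and two-sided 5%. Also assumed: full retention and e12 = e6. The rejection probability is P(|N(|s1|/SE, 1)| > 1.96).

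| Setting | SE | drift 0 | 0.05 | 0.10 | 0.20 | 0.30 |
|---|---|---|---|---|---|---|
| Equal SD of change, n = 150 | sqrt(2/150) = 0.115 | 0.050 | 0.072 | 0.139 | 0.410 | 0.738 |
| Equal SD of change, n = 105 (assumed) | sqrt(2/105) = 0.138 | 0.050 | 0.065 | 0.112 | 0.305 | 0.585 |
| 12-month change has twice the variance, drift in 12-month SDs, n = 150 | sqrt(1.5/150) = 0.100 | 0.050 | 0.079 | 0.170 | 0.516 | 0.851 |
| Same, drift in 6-month SDs, n = 150 | sqrt(3/150) = 0.141 | 0.050 | 0.064 | 0.109 | 0.293 | 0.564 |

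A simulation (6,000 runs per setting, visit correlation 0.5, n = 150) agrees. Drift of -0.20 rejects 0.405, almost always against the longer duration. Drift of +0.20 rejects 0.406, almost always in its favour. Comparing month-12 scores adjusted for baseline rejects 0.046 to 0.054 for drift from -0.30 to +0.30.

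**Masking.** A true difference of 0.325 SD has 80% power at n = 150 with no drift. With drift of -0.20 the expected contrast is 0.325 - 0.20 = 0.125 SD. Simulated power is then 0.187, against 0.894 for the adjusted month-12 comparison.

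**Utilization: which window?** Suppose support lowers the rate by a constant delta while it is given, with no benefit of duration. Over months 0-12 the immediate arm averages -delta and the delayed arm -delta/2, a contrast of -delta/2 that is not a dose effect. With delta = 0.209 SD (the SAP's effect size, as illustration) this is 0.1045 SD and rejects 0.148 of the time at n = 150. Over months 6-12 both arms are supported and the contrast is 0, also under a common trend, provided retention is complete.

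**The case against.** The strongest objection is that the finding is conditional. If AJFCS ran the matched design in the protocol, there is no delayed-support arm and the contrast does not exist. This stands as a condition, but it does not rescue the analysis, which would then have no basis.

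The sizes rest on assumption. Nothing in the documents supports drift of 0.20 to 0.30 SD over a negligible value, and at zero drift the test keeps its 5% level. The 150 per arm is a protocol goal attached to the matched recruitment plan. The three site goals sum to 226 + 300 + 60 = 586, not the SAP's 720. The percentages are therefore illustrations. The extra term s1 does not depend on them.

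The consequence is limited: one site, a secondary question, and no demonstrated effect on the primary utilization outcome. That is fair and is reflected in the grading.

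On the remedy, the zero contrast for the months 6-12 rate ignores selection: if support prevents early exits, the arms differ in frailty by month 6. With gamma frailty of variance 0.5 to 2, 5-20% early exits and a constant 20-40% effect (all assumed), the rate ratio is about 1.005 to 1.17 with no duration benefit. This is usually small, but it must be disclosed.

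The month-12 survey has the same 8-week late allowance as the month-6 survey. That applies to both arms alike, whereas a late month-6 score would be the starting point of the delayed arm only. Whether support had begun by then is unknown.

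**Conclusion.** The concern holds, with high confidence in the algebra, and should be fixed. Under the SAP's randomized design with a month-6 switch, analysis (3) does not estimate the 12- versus 6-month difference for self-rated scores unless the unsupported change in months 0-6 is zero, which the documents neither state nor assume. At 150 per arm with equal SDs, the false-positive rate runs from 5% with no drift to 74% at 0.30 SD per six months, and a decline of 0.20 SD would cut 80% power to about 19%. Drift, SD structure and full retention are assumptions, and the direction is open. For utilization and placement the planned change in rates is undefined and no size is claimed. Analysis (1), at 6 months, is unaffected.

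**What to change.** 1. Reconcile the protocol's AJFCS recruitment and Matching sections with the SAP's Analysis Plan and Randomization and matching. If there was no randomized switch, delete analysis (3).
2. Otherwise, for self-rated scores, compare month-12 values between the randomized arms, adjusted for the randomization baseline. At n = 150 and visit correlation 0.5 the detectable difference at 80% power is about 0.28 SD, against 0.325 SD for a two-sample comparison of changes. This also avoids the month-6 score as a starting point.
3. For utilization and placement, use the annualized rate over months 6-12 in both arms as the duration comparison. Report the 0-12 month rate only as immediate versus delayed support.
4. State the limits. Duration and start time stay tied together. The months 6-12 rate covers only those still followed at month 6 and rests on half a year of data: its detectable difference at n = 150 is 0.325 SD if its SD equals that of a 12-month rate, or 0.459 SD if its variance is doubled (assumed range).
5. Extend the missing-data and competing-event handling to exits for a main outcome or a move to higher care, since these participants will lack month-12 scores.

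The cost is the design reconciliation, new SAP wording for analysis (3) and a written rule for month-12 scores missing after such exits. No new data collection is needed: the baseline and month-12 surveys and the utilization follow-up are already scheduled.

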Appendix	
Introductory Letter for Participants (Community Place, AJFCS, JFS of LA)	
Failed Contact Recruitment Letter (Community Place)	
Reminder Letter (Community Place, AJFCS)	
Failed Contact 3, 6, 9, 12 month data collection (Community Place)	

Recruitment Strategies

Community Place

Community Place currently has 210 people receiving peer to peer support and 408 people on the wait list to receive peer to peer support. These numbers are fluid. All people in both groups have access to all other services that community place offers older adults in their community such as access to the Senior Center, various services we can connect with through our caseworker (Home delivered meals, benefits eligibility, Catholic Family Center-Elder one, Food link, Clothing services, legal consulting services, and Life span (Financial Budgeting, caregivers plan, HEP, High Cap-Health Insurance, Elder abuse prevention, and Rep pay program)).

All the people that are in the correct age range (≥ 65 years old) and have no known cognitive impairment will be uploaded into the study database in DatStat. People receiving peer to peer support will receive ID Numbers R100E to R499E and people receiving standard community services (on the wait list to receive peer to peer support) will receive ID numbers R500C to R999C. The following variables or a subset of these variables will be uploaded for all participants: ID, First Name, Last Name, Mailing Address, Phone, Age, Date of birth, gender, race, language preference, P2P program type, peer companion name, study group, RA first name, RA last name, RA telephone, RA email, Site PI.

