For Community Place and Alpert Jewish Family and Children's Service (AJFCS), we are matching participants on the following characteristics: age group (<70, 70-80, and ≥ 80 years), gender (male and female), race/ethnicity (African American, Hispanic, and non-Hispanic White) and at Community Place we are also matching based on County (Monroe or Livingston).

At both all sites we are going to recruit people from the waiting list and match them with people already receiving peer to peer services. Every month research staff at UW will ask to see the matching spreadsheet as a way to monitor how matching is progressing at each site.

Enrolling more than one person per household (added 1/14/2016)

As of February 22, 2016, we will only enroll one person per household. This is the protocol for determining which person from the household we will enroll.

- a. If Participant A is enrolled in the study (signed the consent form) and they say they would like their partner would like to participate, the research staff person will let them know that according to study protocol we are only allowed to enroll one person per household. Participant A will be the person that is enrolled in the study.
- b. If prior to enrollment a study staff person is informed that both partners in a couple want to participate in the study. The staff person will let the two participants know that we can only enroll one participant from the couple. If we only need one person then the research staff will screen and enroll that person.
- c. If we know in advance there is a couple interested in participating and both people are needed for the study then we will randomly select one person per household. In this case you should screen both participants. If both participants are deemed eligible to participate you should first assign one participant heads and one participant tails. Then you should pull out the randomization envelope and open it. This envelope will tell you which participant you will enroll. At this time you will discard the envelope.

Enrollment in Study

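### The SAP analyses every participant as independent and makes no provision for clients who may share a peer companion, or for couples who may have enrolled before the one-per-household rule

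*SAP*

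**What the plan says.** The SAP's Analysis Plan states: "The primary analyses for comparative effectiveness will be based on two-sample independent tests". It names the t-test, Wilcoxon rank sum, Fisher's exact and chi-square tests, and adds: "These tests will be performed at a two-tailed significance level of 0.05 without adjustment for multiplicity". Adjusted linear, logistic or Poisson regressions follow, with the stratification factors and a site indicator as covariates. Mixed-effects models appear only for the exploratory mediation work, and no level of clustering is named for them. Neither document mentions companion or household clustering, robust errors or a design effect.

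The Sample Size Justification begins "Given the total sample size of 720 at-risk older adults" and continues: "the study has 0.80/0.85/0.90 power to detect the effect size of 0.209/0.223/0.242". The effect size is standardised by the "standard deviation of the annualized rate assumed to be common in the two groups". Drop-out and death are named as reasons for lower power; dependence between participants is not.

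In the Protocol, the variables that may be uploaded for Community Place include "P2P program type, peer companion name, study group", but the list is introduced as all of these variables or only some of them. The AJFCS upload fields do not include the companion, and the JFSLA fields are not stated. The section on enrolling more than one person per household says: "As of February 22, 2016, we will only enroll one person per household".

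**The concern.** A client's experience of peer support depends partly on who the companion is: how often that person visits, and how well. Clients of the same companion may therefore have correlated outcomes. Controls on standard services have no companion, so the dependence would lie in one arm only. A couple enrolled before the household rule would be a second, smaller source.

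A two-sample test that ignores positive within-companion correlation understates the variance of the peer-arm mean. Intervals are then too narrow, the test rejects too often under the null, and the stated power is optimistic. The adjusted regressions do not cure this, because covariates for site, age, gender and race/ethnicity do not identify the companion.

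**Working it through.** **Inputs from the documents.** Total N 720, two-sided 0.05, standardised effects 0.209/0.223/0.242, common SD (SAP, Sample Size Justification). Equal arms are taken as 360 each: AJFCS allocates "in a 1:1 ratio using permuted block randomization, stratified by age, gender and race/ethnicity" and the Protocol's site goals are equal per arm. Those goals sum to 226 + 300 + 60 = 586, not 720. That is a separate matter, and 720 is used throughout here.

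**Inputs that had to be assumed.** Enrolled clients per companion m (2 to 5, with 10 as an extreme), ICC (0.02 to 0.10), share of participants in couples f (2% to 10%) and within-couple correlation r (0.1 to 0.3). The documents give none of these.

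**Step 1: the plan's own figure.** With independent participants, power = Φ(ES × √(360/2) − 1.96). For 0.209: 0.209 × 13.416 = 2.804, and Φ(0.844) = 0.801. The other two effects give 0.849 and 0.901. The stated 0.80/0.85/0.90 reproduce, so the power statement is an independent-observations calculation with no design effect.

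**Step 2: companion clustering in the peer arm only.**
- Peer-arm design effect DE = 1 + (m − 1) × ICC.
- Ratio of true to naive SE = √((1 + DE)/2).
- True level of the naive test = 2 × (1 − Φ(1.96/SE ratio)).
- Power at 0.209 with the correct SE = Φ(2.804/SE ratio − 1.96).

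Example, m = 5 and ICC 0.10: DE = 1.40; SE ratio = √1.20 = 1.095; 1.96/1.095 = 1.79, so the level is 7.4%; 2.804/1.095 − 1.96 = 0.60, so power is 0.726.

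| m | ICC | DE | SE ratio | True level | Power at 0.209 |
|---|---|---|---|---|---|
| 1 | any | 1.00 | 1.000 | 5.0% | 0.801 |
| 2 | 0.02 | 1.02 | 1.005 | 5.1% | 0.797 |
| 2 | 0.10 | 1.10 | 1.025 | 5.6% | 0.781 |
| 5 | 0.02 | 1.08 | 1.020 | 5.5% | 0.785 |
| 5 | 0.05 | 1.20 | 1.049 | 6.2% | 0.762 |
| 5 | 0.10 | 1.40 | 1.095 | 7.4% | 0.726 |
| 10 | 0.05 | 1.45 | 1.107 | 7.7% | 0.717 |

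**Step 3: couples.** DE = 1 + f × r if partners are in the same arm and 1 − f × r if they are in opposite arms. At the top of the range, f × r = 0.10 × 0.3 = 0.03. Same-arm couples give an SE ratio of √1.03 = 1.015 (level 5.3%). Opposite-arm couples give √0.97 = 0.985 (level 4.7%, conservative).

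**Step 4: which analyses have clustering in one arm only.** Up to 6 months AJFCS controls receive standard services, so Step 2 applies. The SAP then moves them to peer support between 6 and 12 months. In the AJFCS comparison of 12 with 6 months of support, both groups have companions, possibly the same ones, and the one-arm formula does not apply.

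**The case against.** A reader might infer that the standard errors are certainly too small and that the 5% level is breached. The documents do not support that. They give no number of companions, no caseload and no statement that a companion serves more than one enrolled client. The household rule implies that couples could have been enrolled earlier, but not that any were.

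The net direction is also open. Matching at the non-randomized sites and stratified randomization at AJFCS, if ignored in an unpaired test, tend to make it conservative when the factors predict outcome. Couples split across arms do the same. This stands, but an unquantified error in the other direction is no safeguard. The adjusted regressions include the stratification factors, which should remove much of that cushion and leave any companion effect in place.

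The calculation needs enrolled clients per companion, not total caseload. Peer-arm goals are 113 + 150 + 30 = 293 of about 210 + 205 + 57 = 472 current clients, or 62%. If enrolment is spread evenly over companions (an assumption), a total caseload of 5 at ICC 0.10 gives DE = 1 + 4 × 0.62 × 0.10 = 1.248 and SE ratio √1.124 = 1.060, a level of about 6.5% rather than 7.4%. The table is therefore to be read with m as enrolled clients.

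It is also tempting to say that the cluster identifier is already in the database. That is documented for Community Place only, and with a qualifier. AJFCS and JFSLA account for 360 of the 586 in the site goals (61%).

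**Conclusion.** The gap is real: no confirmatory analysis allows for dependence within companion or household, and the power figures assume there is none. Its consequence is conditional. If companions serve 2 to 5 enrolled clients and the ICC is 0.02 to 0.10, the true level of the naive test is about 5.1% to 7.4%, and power at 0.209 is about 0.80 to 0.73 instead of 0.80. If each companion has one enrolled client, or the ICC is zero, the companion effect vanishes. Couples are a minor matter, at most about 1.5% of the standard error over the assumed range and of either sign. These figures rest on assumed caseloads and correlations, equal caseloads, and 360 per arm for the power column. This is a modest improvement to the plan, not a defect that by itself undermines the trial's conclusions.

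**What to change.** Fit the between-group comparisons as regression models with cluster-robust standard errors, or as a partially nested model. Robust errors cannot simply be attached to Fisher's exact or the standard rank-sum test, so the regression has to carry the inference. If the sponsor keeps the simple tests as primary, the clustered model should at least be a prespecified sensitivity analysis.

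- Up to 6 months, cluster on companion in the peer group and treat controls as single-person clusters.
- Merge members of one household into a single cluster, including any couple split across arms or companions.
- In the AJFCS comparison of 12 with 6 months, cluster on companion in both groups.
- Report enrolled clients per companion at each site and the number of couples enrolled before February 22, 2016.
- State in the Sample Size Justification that the power figures assume independent participants.
- For site subgroups, use a small-sample correction. At JFSLA, for example, 30 peer clients at 5 per companion would be only 30/5 = 6 clusters.

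The cost is a short SAP amendment and slightly wider intervals where dependence exists. AJFCS and JFSLA would have to supply companion identity from agency records, and Community Place should confirm that its field was uploaded. Household can be derived from address where that is recorded: it is among Community Place's listed fields, and AJFCS adds it once a participant agrees to take part.
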